12.2.3 Unsolicited Adverse Events

Participants will be instructed to contact the study site and report any adverse events up to 30 days post vaccine administration. This will include any delayed onset local reactions.

12.2.4 Adverse Events of Special Interest (AESI)

Any case of myocarditis or pericarditis within 6 weeks after study vaccination will be reported as an AESI. Regardless of seriousness, these events will be reported to DAIT/NIAID within 24 hours of awareness on the Serious Adverse Event case report form.

For myocarditis and pericarditis events, any relevant laboratory information, imaging (echocardiography, cardiac MRI) and/or pathology (cardiac biopsy) results will be reported on case report forms. The DAIT medical monitor may require that appropriately deidentified copies of studies, including but not limited to EKG, imaging, cardiac biopsies digital images, or other follow-up results (stress tests results) be made available for medical monitor or ad hoc DSMB review.

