13.4.4	Analyses of Exploratory Objectives	53
13.4.5	Descriptive Analyses	53
13.5	Interim Analyses	53
13.5.1	Interim Analysis of Efficacy Data	53
13.5.2	Interim Analysis of Safety Data	53
13.6	Statistical Hypotheses	53
13.7	Sample Size Considerations	53
14.	Identification and Access to Source Data	55
14.1	Source Data	55
14.2	Access to Source Data	55
15.	Quality Assurance and Quality Control	56
16.	Protocol Deviations	57
16.1	Protocol Deviation Definitions	57
16.2	Reporting and Managing Protocol Deviations	57
17.	Ethical Considerations and Compliance with Good Clinical Practice	58
17.1	Statement of Compliance	58
17.2	Informed Consent Process	58
17.3	Privacy and Confidentiality	58
18.	Publication Policy	59
19.	References	60

Appendix 1: Screening (All Participants)	65
Appendix 2: Schedule of Events (COVID-19 Vaccine Dose Alone).....	66
Appendix 3: Schedule of Events (IS Reduction plus COVID-19 Vaccine Dose).....	67

Glossary of Abbreviations

ATG	Anti-thymocyte globulin
CFR	Code of Federal Regulations
CRF	Case Report Form
CTCAE	Common Terminology Criteria for Adverse Events
DAIT	Division of Allergy, Immunology, and Transplantation
dnDSA	De novo Donor Specific Antibody
DSA	Donor Specific Antibody
EUA	Emergency Use Authorization
DSMB	Data Safety Monitoring Board
FDA	Food and Drug Administration
GCP	Good Clinical Practice
ICH	International Conference on Harmonization
IND	Investigational New Drug
IRB	Institutional Review Board
IS	Immunosuppression
MOP	Manual of Procedures
NIAID	National Institute of Allergy and Infectious Diseases
PI	Principal Investigator
PrEP	Pre-Exposure Prophylaxis
SAE	Serious Adverse Event
SAP	Statistical Analysis Plan
SAR	Suspected Adverse Reaction
SOP	Standard Operating Procedure
SOT	Solid Organ Transplant
SUSAR	Serious Unexpected Suspected Adverse Reaction
ULN	Upper Limit of Normal

Study Definitions Page

Acute Rejection	
Acute Cell-Mediated Rejection, Biopsy Proven: Rejection (including borderline) graded according to 2019 Banff Criteria.
 
Antibody-Mediated Rejection: A clinical and histologic event that meets the Banff 2019 criteria for antibody mediated rejection.
 
Clinically Diagnosed and Treated Rejection: Any clinical event, with or without supporting evidence from a biopsy, which the treating physician diagnoses as “rejection” AND for which the patient is treated with steroids, lytic therapy, or an increase in dose or number of immunosuppressive medications.

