11.5 Study Pausing Rules

If the following occur, relevant study interventions will be temporarily halted pending a DSMB review and recommendation as to whether the study may proceed.

1. Any Grade 4 or 5 event that is definitely or possibly attributed to the study dose of vaccine or to immunosuppression reduction.
2. Any probable or confirmed case of either acute myocarditis or acute pericarditis that occurs within 6 weeks of the study vaccine.
3. **Excess incidence of acute rejection (clinically treated or biopsy-proven):** Based on registry data, approximately 5-6 rejection events would be expected over the course of the study, independent of any effect of the study interventions. A pausing rule has been constructed such that the study would be paused if there is a >50% chance that the observed event rate exceeds three times the expected rate. The pausing rule will be applied to the study by group: (1) COVID-19 vaccine dose alone (2) MMF withdrawal (3) CNI reduction. Event rates triggering a pause are shown below:

Number of participants	Number of events required to trigger a pause	Event rate required to trigger a pause
10	3	30%
20	3	15%
30	3	10%
40	4	10%
50	4	8%
75	4	5%
100	5	5%
150	6	4.0%

200	7	3.5%
250	8	3.2%
300	9	3.0%
350	10	2.9%
400	11	2.8%

4. **Excess incidence of graft loss:** Based on registry data, it is expected that there will be approximately 6-7 graft losses over the course of the study, independent of any effect of the study interventions. A pausing rule has been constructed such that the study would be paused if there is a >50% chance that the observed event rate exceeds three times the expected rate. The pausing rule will be applied to the study by group: (1) COVID-19 vaccine dose alone (2) MMF withdrawal (3) CNI reduction. Event rates triggering a pause are shown below:

Number of participants	Number of events required to trigger a pause	Event rate required to trigger a pause
10	3	30%
20	3	15%
30	3	10%
40	4	10%
50	4	8%
75	4	5%
100	5	5%
150	6	4.0%
200	7	3.5%
250	8	3.2%
300	9	3.0%
350	10	2.9%
400	11	2.8%

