12.2.7 Serious Adverse Event (SAE)

An adverse event or suspected adverse reaction is considered “serious” if, in the view of either the investigator or Sponsor DAIT/NIAID, it results in any of the following outcomes (21 CFR 312.32(a)):

1. Death.
2. A life-threatening event: An AE or SAR is considered “life-threatening” if, in the view of either the investigator or Sponsor [DAIT/NIAID], its occurrence places the subject at immediate risk of death. It does not include an AE or SAR that, had it occurred in a more severe form, might have caused death.
3. Inpatient hospitalization or prolongation of existing hospitalization.
4. Persistent or significant incapacity or substantial disruption of the ability to conduct normal life functions.
5. Congenital anomaly or birth defect.
6. Important medical events that may not result in death, be life threatening, or require hospitalization may be considered serious when, based upon appropriate medical judgment, they may jeopardize the subject and may require medical or surgical intervention to prevent one of the outcomes listed above.

Elective hospitalizations or hospital admissions for the purpose of conduct of protocol mandated procedures are not to be reported as an SAE unless hospitalization is prolonged due to complications.

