12.5 Reporting of Serious Adverse Events and Adverse Events

12.5.1 Reporting of Serious Adverse Events to DAIT/NIAID

This section describes the responsibilities of the site investigator to report serious adverse events to the sponsor via the AE/SAE eCRF. Timely reporting of adverse events is required by 21 CFR and ICH E6 guidelines.

Site investigators will report all serious adverse events (see Section 12.2.3, *Serious Adverse Event*), regardless of relationship or expectedness within 24 hours of discovering the event.

For serious adverse events, all requested information on the AE/SAE eCRF provided. However, unavailable details of the event will not delay submission of the known information. As additional details become available, the AE/SAE eCRF will be updated and submitted. Initial SAE eCRFs should include as much information as possible, but at a minimum:

- AE term
- Relationship to study vaccination
- Relationship to study procedure
- Reason why the event is serious

- Supplementary eCRF pages that are current at the time of the SAE reporting e.g. medical history and vaccine administration

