12.7 Review of Safety Information

12.7.1 Medical Monitor Review

The NIAID Medical Monitor shall receive monthly reports from the SACCC compiling new and accumulating information on AEs and SAEs recorded by the study site(s) on appropriate eCRFs.

In addition, the Medical Monitor shall review and make decisions on the disposition of the SAE and pregnancy reports received by the SACCC (See Sections 12.5.1, Reporting of Serious Adverse Events to Sponsor, and 12.6, Pregnancy Reporting).

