13.5.2 Interim Analysis of Safety Data

Excess incidence of dnDSA in kidney transplant recipients: An interim analysis will be performed to look for evidence of an excess incidence of dnDSA in the IS reduction groups (those undergoing withdrawal of MMF; and those undergoing a decrease in CNI dose) as compared with those receiving an additional dose of vaccine alone. When fifteen subjects in each of these groups have reached day 30 in the study (study visit 4), the core HLA lab will determine whether de novo DSA is present. We will perform a similar analysis when fifty subjects in each group have reached day 30. At each of these two time points, the proportion with Class II dnDSA in each IS reduction group will be compared with the COVID-19 vaccine dose alone group using a one-sided Fisher exact test to determine if there is an excess incidence of Class II dnDSA, and the results presented to the DSMB for review

[figure not shown]

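### A rejection not judged serious counts toward a pausing rule but has no mandatory 24-hour report to the sponsor, so the pausing count can lag behind new starts of immunosuppression reduction

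*Combined protocol and SAP*

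**What the plan says.** - **Pausing rule (11.5, item 3).** Acute rejection, whether clinically treated or biopsy-proven, is counted in three groups: vaccine alone, MMF withdrawal and CNI reduction. The trigger is 3 events at 10, 20 or 30 participants, 4 at 40 to 75, 5 at 100 and 7 at 200. Graft loss has its own by-group rule with the same table (item 4).
- **What counts as rejection (Study Definitions Page).** Borderline biopsies count. So does a physician's clinical diagnosis, with or without biopsy support, "for which the patient is treated with steroids, lytic therapy, or an increase in dose or number of immunosuppressive medications". Admission is not required.
- **What counts as graft failure (same page).** Re-listing for transplantation is enough on its own, for kidney or liver.
- **The two 24-hour clocks.** Serious adverse events go to the sponsor "regardless of relationship or expectedness within 24 hours of discovering the event" (12.5.1). The special-interest list in 12.2.4 reads: "Any case of myocarditis or pericarditis within 6 weeks after study vaccination will be reported as an AESI". For that list the rule is: "Regardless of seriousness, these events will be reported to DAIT/NIAID within 24 hours of awareness on the Serious Adverse Event case report form".
- **Everything else.** Adverse events are recorded on the eCRF (12.4.3). Then "The NIAID Medical Monitor shall receive monthly reports from the SACCC compiling new and accumulating information on AEs and SAEs" (12.7.1).
- **DSMB (12.7.2).** The first planned review is one month after all participants have been vaccinated. Earlier reviews are discretionary, or follow once a pausing rule has been met.

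**The concern.** A pausing rule works only as fast as its events are counted. Myocarditis and pericarditis are pausing events, and the plan makes them reportable in 24 hours whether serious or not. Deaths and life-threatening events are serious by definition. Rejection and graft loss are also pausing events but have no such guarantee, although section 5.3 names rejection as the risk of reducing immunosuppression and section 5.4 expects no new alloimmune events from the vaccine. Expedited reporting thus covers the special risk of the vaccine, which both arms receive, and leaves out the special risk of the randomised intervention.

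The triggers are small. With a threshold of 3, one event not yet known to the person keeping the count is a third of the trigger. While it is missing, more participants can begin reduction.

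**Working it through.** **1. The plan's own thresholds.** The rejection table is said to follow from a better than even chance that the rate exceeds three times the expected 5 to 6 events. Three times that is 15 to 18 events at 400 participants; the table prints 11, which is 2.0 × 5.5. The table therefore does not reproduce from its stated rule. That is a separate matter, and the printed thresholds are taken as they stand below.

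**2. Following one event through the text.** Take a rejection diagnosed clinically and treated as an outpatient.

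| Question | Answer | Source |
|---|---|---|
| Does it count toward a pause? | Yes | Study Definitions Page; 11.5 item 3 |
| Is it on the 24-hour special-interest list? | No | 12.2.4 |
| Is it an SAE? | Not through admission; only if judged an important medical event or another criterion is met | 12.2.7 |
| If not an SAE, is there a timed report from site to sponsor? | None stated | 12.4.3, 12.5.1 |
| Scheduled route | Monthly report to the Medical Monitor | 12.7.1 |
| Stated eCRF entry deadline, owner of the tally, or checking frequency | None | 11.5, 12 |

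Graft failure met by re-listing alone gives the same answers, taking graft loss in 11.5 to mean Graft Failure as defined.

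The adverse event window adds to this. Under 12.4.1 collection ends at Day 30 with vaccine alone and at about Day 44 with reduction (Day 14 + 30 days). The rejection endpoint runs to Day 60. A later non-serious rejection rests on the rejection entry in the schedules of events (Appendices 2 and 3).

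**3. Size of a lag.** Inputs: 200 participants in the reduction arm (13.7); accrual 4 months (Synopsis). The assumptions are even accrual and entry in time for the next monthly report.

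Starts per month = 200 / accrual months. Extra starts = starts per month × lag in months. A full cycle is the maximum; an event falling at random within a cycle waits half of it on average.

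| Accrual | Starts per month | 24-hour report | Half cycle | Full cycle |
|---|---|---|---|---|
| 4 months (stated) | 200/4 = 50 | 50/30.4 ≈ 1.6 | 25 | 50 |
| 12 months (assumed) | 200/12 ≈ 16.7 | ≈ 0.5 | ≈ 8 | ≈ 17 |
| 24 months (assumed) | 200/24 ≈ 8.3 | ≈ 0.3 | ≈ 4 | ≈ 8 |

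These figures combine the MMF and CNI groups, which the rule monitors separately. The split is not given; at an assumed even split each figure halves.

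**4. Effect on when a pause occurs.** A simulation of 4,000 runs compared 1-day with month-end reporting at 4-month accrual. It treated reduction as one group, every rejection as non-serious and diagnosis as uniform over 0 to 60 days, and applied the next printed table row. Mean number started at the pause (200 if none):

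| True rejection rate | 1-day | Month-end | Difference |
|---|---|---|---|
| 1.4% (expected) | 199.7 | 199.9 | 0.2 |
| 4.1% (3 × 5.5/400) | 177 | 187 | 10 |
| 8% | 118 | 146 | 28 |
| 12% | 87 | 119 | 32 |
| 20% | 62 | 90 | 28 |

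With 12-month accrual the difference was about 10 to 12 for true rates of 4.1% and above. Both assumptions, one group and no serious rejections, push the differences up.

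**The case against.** The strongest reply is that the documents do not say the pausing counts are updated monthly. Section 12.7.1 describes a report to the Medical Monitor, not the tally. Rejection and graft loss have their own entry in the schedules, apart from AE and SAE, and the data centre may watch those forms daily. That stands: the monthly lag is the longest interval implied by the one scheduled route, not a documented delay.

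A reader might infer that an outpatient rejection has no 24-hour reporting at all. The documents do not support that. Section 12.2.7 lets investigator or sponsor judge an event serious as an important medical event, and the 24-hour clock then applies. An admission makes it serious outright. The sponsor's judgement, however, can operate only once the sponsor knows of the event, so this route rests on the site's discretion. Pausing rule 1 catches Grade 4 or 5 events attributed to reduction, but not milder treated rejection.

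A reader might also infer that many more participants will certainly start reduction before a pause. The 50-per-month figure depends on the 4-month accrual. Section 6 shows the study vaccine changing twice across protocol versions, which makes that pace doubtful.

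Nor should the point extend to donor-specific antibody or IS Reduction Failure. Neither is a pausing event in 11.5, and the second by definition excludes treated rejection. Section 13.5.2 describes a group comparison for the DSMB and does not say how individual results are returned.

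Finally, individual participants are monitored: weekly graft tests and contact with the site (8.3.3, 8.4), and repeat testing under 6.12. Sites should therefore learn of rejection quickly. The missing step is from site to sponsor.

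**Conclusion.** The gap holds as a textual fact. Rejection and graft loss drive by-group pausing rules, yet a rejection not judged serious, or a graft failure met by re-listing alone, has no mandatory timed report to the sponsor.

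Its cost is bounded. At the stated accrual, a full monthly cycle allows at most about 50 extra starts of reduction and about 25 on average, across both reduction groups. At an assumed 12 or 24 months the maximum is about 17 or 8. The true figure is smaller within each group, if some rejections are SAEs, or if the eCRF is checked more often than monthly. It could be larger if sites enter events late, since no entry deadline is stated. If rejection stays at the expected rate the delay costs almost nothing; it matters when reduction raises the rate, which is the case the rule exists for. This is a cheap improvement to a safety rule and not a flaw in the primary comparison.

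**What to change.** In 12.2.4, add every rejection meeting the study definition, and graft loss, in both arms, as events reported to DAIT/NIAID within 24 hours of awareness regardless of seriousness, on the form already used for myocarditis and pericarditis. State the period covered; it should at least span the 60-day endpoint window, so that it does not stop with adverse event collection. In 11.5, state that the data centre updates the by-group pausing counts at each such report.

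The cost is expedited forms for about 5 to 6 rejections plus 6 to 7 graft losses expected study-wide (11 to 13 in all), and more only if the rates rise. There is no new procedure and no change to clinical management.

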12.2.5 Suspected Adverse Reaction (SAR)

Any adverse event for which there is a reasonable possibility that the SARS-CoV-2 vaccine caused the adverse event. For the purposes of safety reporting, 'reasonable possibility' means there is evidence to suggest a causal relationship between the drug and the adverse event. A suspected adverse reaction implies a lesser degree of certainty about causality than adverse reaction, which means any adverse event caused by a drug (21 CFR 312.32(a)).

12.2.6 Unexpected Adverse Event

An adverse event or suspected adverse reaction is considered "unexpected" if it is not consistent with the risk information described in Vaccine-specific FDA EUA Full Prescribing Information) (21 CFR 312.32(a) and 310.305)

12.2.7 Serious Adverse Event (SAE)

An adverse event or suspected adverse reaction is considered “serious” if, in the view of either the investigator or Sponsor DAIT/NIAID, it results in any of the following outcomes (21 CFR 312.32(a)):

1. Death.
2. A life-threatening event: An AE or SAR is considered “life-threatening” if, in the view of either the investigator or Sponsor [DAIT/NIAID], its occurrence places the subject at immediate risk of death. It does not include an AE or SAR that, had it occurred in a more severe form, might have caused death.
3. Inpatient hospitalization or prolongation of existing hospitalization.
4. Persistent or significant incapacity or substantial disruption of the ability to conduct normal life functions.
5. Congenital anomaly or birth defect.
6. Important medical events that may not result in death, be life threatening, or require hospitalization may be considered serious when, based upon appropriate medical judgment, they may jeopardize the subject and may require medical or surgical intervention to prevent one of the outcomes listed above.

Elective hospitalizations or hospital admissions for the purpose of conduct of protocol mandated procedures are not to be reported as an SAE unless hospitalization is prolonged due to complications.

12.3 Grading and Attribution of Adverse Events

12.3.1 Grading Criteria

The study site will grade the severity of adverse events experienced by the study subjects according to the criteria set forth in the National Cancer Institute’s Common Terminology Criteria for Adverse Events (CTCAE) Version 5.0. This document (referred to herein as the NCI-CTCAE manual) provides a common language to describe levels of severity, to analyze and interpret data, and to articulate the clinical significance of all adverse events. The NCI-CTCAE has been reviewed by the NIAID Medical Monitor and Protocol Chair and has been deemed appropriate for the subject population to be studied in this protocol.

Adverse events will be graded on a scale from 1 to 5 according to the following standards in the NCI-CTCAE manual:

Grade 1 = Mild; asymptomatic or mild symptoms; clinical or diagnostic observations only; intervention not indicated.

Grade 2 = Moderate; minimal, local or noninvasive intervention indicated; limiting age appropriate instrumental activities of daily living (ADL: Instrumental ADL refer to preparing meals, shopping for groceries or clothes, using the telephone, managing money, etc.)

Grade 3 = Severe or medically significant but not immediately life-threatening; hospitalization or prolongation of hospitalization indicated; disabling; limiting self-care activities of daily living (ADL: Self-care ADL refer to bathing, dressing and undressing, feeding self, using the toilet, taking medications, and not bedridden.)

Grade 4 = Life-threatening consequences; urgent intervention indicated.

Grade 5 = Death related to AE.

For grading an abnormal value or result of a clinical or laboratory evaluation (including, but not limited to, a radiograph, an ultrasound, an electrocardiogram etc.), a treatment-emergent adverse event is defined as an increase in grade from baseline or from the last post-baseline value that doesn't meet grading criteria. Changes in grade from screening to baseline will also be recorded as adverse events but are not treatment-emergent. If a specific event or result from a given clinical or laboratory evaluation is not included in the NCI-CTCAE manual, then an abnormal result would be considered an adverse event if changes in therapy or monitoring are implemented as a result of the event/result.

12.3.2 Attribution Definitions

The relationship, or attribution, of an adverse event to the study therapy regimen or study procedure(s) will initially be determined by the site investigator and recorded on the appropriate AE/SAE eCRF. Final determination of attribution for safety reporting will be determined by DAIT/NIAID. The relationship of an adverse event to study therapy regimen or procedures will be determined using the descriptors and definitions provided in Table 12.3.2.

For additional information and a printable version of the NCI-CTCAE manual, consult the NCI-CTCAE web site: <http://ctep.cancer.gov/reporting/ctc.html>.

Table 12.3.2 Attribution of Adverse Events

Code	Descriptor	Relationship (to primary investigational product and/or other concurrent mandated study therapy or study procedure)
UNRELATED CATEGORY		
1	Not Related	The adverse event is clearly not related: there is insufficient evidence to suggest a causal relationship.
RELATED CATEGORIES		
2	Possibly Related	The adverse event has a reasonable possibility to be related; there is evidence to suggest a causal relationship.
3	Related	The adverse event is clearly related.

